2.4 Risk/Benefit Assessment

2.4.1 Known Potential Risks

PRP therapy has not been studied for nail disease in the past. Risks associated with the use of PRP therapy in the context of hair restoration and skin aging are mostly mild and transient. They include pain, erythema, bruising/ecchymosis, edema, tenderness, scarring, bleeding or infection at the injection site.

2.4.2 Known Potential Benefits

Platelet-rich plasma (PRP) is an autologous concentration of platelets, which can release quantities of growth factors and cytokines. Such a complex of bioactive agents can promote the healing and restoration of multiple tissues when injured. PRP injections have been used to promote hair growth in dermatology and alleviation of joint instability in orthopedics. PRP injections into the nail matrix may promote the growth nails in patients with brittle nails and offer them better functionality.

2.4.3 Assessment of Potential Risks and Benefits

There are currently no consistently effective treatments for brittle nail syndrome. Risks associated with platelet-rich plasma (PRP) therapy for hair restoration and skin aging have been shown to be mostly mild and transient. If PRP is shown to be effective for brittle nail syndrome in this study, patient's quality of life and functionality may significantly improve.

3. Study Design

3.1 Overall Design

This is a single center evaluation of 10 patients with signs and symptoms of brittle nails. Patients will be consented and 8/10 fingernails will be treated with PRP and 2/10 fingernails will be used as controls. Computer software will be used to randomly generate a randomization table for each participant. Randomization for each participant will be done on the same day of their first treatment, after all inclusion and exclusion criteria, including a negative histopathology report for onychomycosis are fulfilled. Blood will be drawn from a vein in the patient's arm into a 11 ml Eclipse PRP Tube. The blood is processed using a centrifuge machine from eclipse medical. After centrifugation, the platelet poor portion will be separated from the platelet-rich portion. The proximal nail folds are cleansed with alcohol. Using a 1ml syringe and 30g needle, 0.1-0.2 ml of platelet-rich plasma is injected into 8 proximal nail folds (treated nails), while 2 proximal nail folds (untreated nails) are injected with platelet-poor plasma. The study patients will be treated with PRP injections monthly for 3 months. Study patients may not have used any medications on the nails 3 months prior to the study or nail polish 1 month prior to the study. The patient must abstain from using any medication, moisturizers, oils, or nail polishes during the study period. The primary efficacy

endpoint will be the individual physician observed Physician Global Improvement Score (PGIA), which encompasses observed improvement of lamellar splitting, transverse splitting, ridges and longitudinal grooves, longitudinal splitting, and nail thickness of target nails. This is a PROBE design- Prospective Randomized Open Label Blinded Endpoint Design, i.e. Treatment is open label with respect to patient and investigators but is blinded to the endpoint committee. High quality images will be obtained utilizing a Canon camera and reviewed by an independent blinded endpoint committee (3 dermatologists with expertise in nails disease [name], [name], and [name] [name]) for PGIA (Physician Global Improvement Assessment. If necessary due to poor image quality (e.g. light source not properly deployed), exposure correction post-imaging may be applied to images that are deemed unsatisfactory. The present study Is not funded, Eclipse Medical provided the required PRP kits, including the sterile tubes.

PGA (Physician Global Assessment) Score:

The Principal Investigator will utilize the Physician Global Assessment (PGA) score for screening purposes during the screening/baseline visit to determine eligibility. The PGA will be comprised of five components: lamellar splitting, transverse splitting, ridging and longitudinal groove, longitudinal splitting, and nail thickness. Lamellar splitting, which represents onychoschizia, is defined as distal furrows or splits encompassing the distal nail plate involving the complete free edge of the nail plate. The second component, transverse splitting, is described as horizontal splitting from the free edge of the nail plate- with at least 2 or 3 horizontal splits of the distal nail plate. The third component, ridging and longitudinal grooves, is defined by at least 50% of the nail plate showing deep ridges and corresponding grooves. The fourth component, longitudinal splitting, which represents onychorrhexis, is defined as at least one deep longitudinal split of the entire nail plate. The fifth component, nail thickness, is defined by a clearly visible change in nail thickness. The presence of each of these components during the screening/baseline visit will represent 1 point on a scale. The inclusion criterion requires patients to have a score of at least 2 out of a maximum of 5 points.

The components used in the PGA assessment have been based on the scoring system used by Van der Kerkhof et. Al in their study, "Brittle nail syndrome: A pathogenesis-based approach with a proposed grading system". In this study, a grading system of 0-3 was used for each component, with 0-none, 1-mild, 2-moderate, 3-severe. The scale used for screening in the present study mirrors the moderate (score of 2) criteria used in the study by van der Kerkhof et. Al.

The Nail Superficial Abnormality Index (NSI):

The surface of the nails is divided into four quadrants, and each quadrant is scored for four parameters, namely, pitting, discoloration, longitudinal ridging and horizontal ridging. The presence or absence of any of these four parameters is scored as 1 or 0, respectively. Thus, the maximum possible score for a nail is 16 and minimum is 0.

Adverse Events and Reporting

Adverse events (AE) assessment will be ongoing throughout the study. All adverse events shall be reported by the clinical Investigator to the IRB as described below.

Adverse Device Effect (ADE)

Any sign, symptom, or disease in a study subject that occurs during the course of a clinical trial that is determined by the investigator to have a causal relationship or possible causal relationship with the device under investigation.

Serious Adverse Event (SAE)

Any untoward medical occurrence in a subject, regardless of whether the event is related to the device that:

- a. results in death;
- b. results in a life-threatening illness or injury;
- c. results in a permanent impairment of a body structure or body function;
- d. requires in-subject hospitalization or prolongation of existing hospitalization
- e. requires a medical or surgical intervention that was necessary to preclude permanent impairment of a body function, or prevent permanent damage to a body structure, either situation suspected to be due to the use of a medical product.
- f. If exposed prior to conception or during pregnancy may have resulted in an adverse outcome in the child.
- g. Does not fit the other outcomes, but the event may jeopardize the patient and may require medical or surgical intervention (treatment) to prevent one of the other outcomes. Examples include allergic bronchospasm (a serious problem with breathing) requiring treatment in an emergency room, serious blood dyscrasias (blood disorders) or seizures/convulsions that do not result in hospitalization. The development of drug dependence or drug abuse would also be examples of important medical events.

Serious adverse events (SAEs) and unanticipated adverse device effects (UADEs) must be reported within 24 hours of knowledge of the event to the IRB.

Unanticipated Adverse Device Effect (UADE) Any serious adverse effect on health and safety or any life-threatening problem or death caused by, or associated with a device, if that effect, problem, or death was not previously identified in nature, severity, or degree of incidence in the investigational plan or application, or any other unanticipated serious problem associated with a device that relates to the rights, safety, or welfare of subjects.

The Investigator shall be responsible for determination of the causal relationship of all adverse events to the device and/or procedure. The Principal Investigator is responsible for monitoring the safety of the subjects enrolled.

Any serious adverse events will be reviewed and analysed by the Principal Investigator as soon as the event occurs and will be documented in the subject's binder.

INVESTIGATIONAL DEVICE SUPPLY

PRP (medical device) will be supplied by Eclipse Medical.

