2.1 Disease

Brittle Nail Syndrome is a heterogeneous abnormality characterized by roughness of the surface of the nail plate, fragility or raggedness of the distal nail, splitting and peeling. It is most frequent in elderly individuals and affects about 20% of the population with women affected twice as frequently as men. Many patients view brittle nails as a cosmetic problem and a substantial number indicate that these nail abnormalities may be painful, may impair daily activities, and may have a negative impact on occupational abilities. Treatment is challenging for the clinician and is dependent upon cooperation of the patient. Treatment of brittle nails is aimed at restoration and maintenance of a normal degree of nail plate hydration by minimizing exposure to dehydrating chemicals and by use of moisturizers, such as alpha-hydroxy acids. There are currently no consistently effective treatments for this condition.

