4.3 Exclusion Criteria

- 1. Inability of the patient to provide written informed consent for any reason.
- 2. Subject has psoriasis, lichen planus, dermatophyte infection or other confounding abnormalities that are severe enough to result in a clinically abnormal fingernail
- 3. Use of any medication within 90 days prior to start of study
- 4. Inability to abstain for nail polishes, nail gels during the study period
- 5. Subject is pregnant or planning pregnancy.

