4.4 Lifestyle Considerations

During this study, participants are asked to:

 Abstain from using any medication, moisturizers, oils, or nail polishes during the study period. Participants that do not fulfill this criterion will be excluded from the study.

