6.1.1 Screening Visit (visit 1)

Screening visit

During the screening visit, all inclusion and exclusion criteria will be reviewed. Obtaining patient consent, history and review of medications will take place. A nail clipping will be obtained for those patients that have not had a negative histopathology result for onychomycosis within the past 6 months. If the patient has had a previous nail clipping within the past 6 months, that will suffice. Therefore, for some patients Visit 1 can take place on the same day of the Screening Visit, while for others Visit 1 will take place on week 2 (after a negative histopathology result for onychomycosis is received).

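### Moisturizers and oils are banned on study but not restricted before baseline, so the effect of stopping them, of unknown size, falls inside the primary before/after change

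*Combined protocol and SAP*

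**What the plan says.** **Before the study.** Section 3.1 says patients "may not have used any medications on the nails 3 months prior to the study or nail polish 1 month prior to the study". Section 4.3 excludes "Use of any medication within 90 days prior to start of study". Its only criterion on cosmetics looks forward: "Inability to abstain for nail polishes, nail gels during the study period". No section sets a pre-study period for moisturizers or oils.

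**During the study.** Section 3.1: "The patient must abstain from using any medication, moisturizers, oils, or nail polishes during the study period". Section 4.4 repeats the list and removes participants who do not comply. Both sections name moisturizers and oils separately from medication, so the 90-day medication rule does not clearly reach them.

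**Why these products may matter.** Section 2.1 describes treatment as aiming at "maintenance of a normal degree of nail plate hydration by minimizing exposure to dehydrating chemicals and by use of moisturizers, such as alpha-hydroxy acids".

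**When baseline can fall.** Under Section 6.1.1, "for some patients Visit 1 can take place on the same day of the Screening Visit"; the others start at week 2, once the histopathology result is back. The schedule in Section 6.1 has photographs at both screening and Visit 1, and no section says which set is the baseline.

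**Analysis.** Section 12.1 compares week 12-14 with baseline within the PRP nails and, separately, within the nails without PRP. Section 12.4.1 only refers back to it.

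**The concern.** A washout is useful when a product that could affect the outcome is withdrawn at study entry. The protocol applies that principle to nail medications and polish but leaves out two other product classes that it bans on study, and gives no reason.

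A participant who moisturizes up to the day of consent, starts that day and then complies fully has a baseline photograph taken on the product and a final photograph taken after about 12 weeks off it. A non-user has no such change. Since the planned test is a pure before/after comparison, whatever stopping does to the nails is counted as part of the PRP effect. The shift belongs to the person and touches all ten nails, so having eight treated nails per person does not average it out.

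It would also be hard to untangle later. Section 6.1.1 has medications reviewed at screening, while cosmetics first appear in the Visit 2 and 3 reviews in Section 6.1.2. Prior moisturizer or oil use need not be recorded.

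**Working it through.** **1. The two product lists side by side**

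| Product | Pre-study limit | On-study ban |
|---|---|---|
| Medication | 3 months on the nails (3.1); 90 days, any (4.3) | Yes (3.1, 4.4) |
| Nail polish | 1 month (3.1; absent from 4.3) | Yes (3.1, 4.3, 4.4) |
| Moisturizers | None | Yes (3.1, 4.4) |
| Oils | None | Yes (3.1, 4.4) |

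**2. Time off product in a compliant user who starts on the screening day.** Before the baseline photograph: possibly 0 days. Before the final photograph: Visit 1 at week 0 to Visit 4 at week 12, about 12 weeks.

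**3. The plan's own figure.** Inputs from Section 12.1: change 0.5, SD 1, two-sided paired t-test, alpha 0.05, power 90%. Power is P(|T| > t(0.975, n-1)), where T is noncentral t with n-1 degrees of freedom and noncentrality (change/SD) x √n. At n = 44 this gives 0.900, and all six cells of the sample-size table reproduce (5, 13, 26, 13, 44, 97). The stated figures are correct for their inputs. With the 80 PRP nails of Section 12.2, power is 0.993.

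**4. Illustration of a shift.** Let f be the share of participants who stop these products and w the mean worsening per user. The mean shift is f x w. The documents give neither, so both are assumed, and zero is a possible value. For example, 0.2 x 0.5 = 0.10 and 0.5 x 0.5 = 0.25. Take a true PRP change of 0.5, SD 1, and nails treated as independent, as the plan does:

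| Mean worsening | Net change | Noncentrality, n = 80 | Power, 80 nails | Power, 44 nails | Nails for 90% power |
|---|---|---|---|---|---|
| 0 | 0.50 | 4.47 | 0.993 | 0.900 | 44 |
| 0.10 | 0.40 | 3.58 | 0.942 | 0.737 | 68 |
| 0.25 | 0.25 | 2.24 | 0.598 | 0.368 | 171 |

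**5. Added noise.** If half the participants are users and each shifts by 0.5, the between-person SD of the shift is √(0.5 x 0.5) x 0.5 = 0.25. Over 10 participants that is a standard error of 0.25/√10 = 0.08, beside the plan's implied 1/√80 = 0.11. The power figures in step 4 leave this out.

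**6. The within-participant contrast.** If all ten nails of a person shift by s, the PRP mean change is (PRP effect + s) and the PPP mean change is (PPP effect + s). Their difference does not contain s.

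**The case against.** The strongest reply is that the gap in the text need not matter in practice, and much of that stands.

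- **Moisturizers as the treatment.** A reader might infer that the ban withdraws the established treatment. Section 2.1 does not say so: moisturizers are one of two named measures, oils are not mentioned, and the section adds that nothing is consistently effective. Section 2.4.3 repeats this. Stopping may do little.
- **A large bias.** A reader might assume a high share of users and a loss of 0.5 to 1 point each, giving a shift as large as the 0.5 the trial is sized for. Nothing in the documents supports either input. The PGA in Section 3.1 is a 0-5 count of coarse structural findings, such as deep ridging over at least half the plate. An average loss of 0.5 would mean every second nail of a user gaining a whole new component. The primary endpoint is mostly called PGIA, for which no 0-5 scale is given.
- **A false claim of benefit.** On the hydration rationale, withdrawal worsens nails. If PRP did nothing, that would show as deterioration, not as success. The likely harm is a missed benefit.
- **Same-day against week-2 starters.** A reader might infer a clean contrast of 0 and 14 days of abstention. That needs the study period to start at screening and the Visit 1 photograph to be baseline, and neither is defined.
- **The internal control.** Two nails per person are randomized to PPP, and a shared shift cancels in a PRP-minus-PPP comparison. This is true of the design, but Section 12.1 does not plan that comparison.

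What remains is that a participant who follows every rule can have different product exposure at the two time points of the primary test, and the analysis has no means of removing it.

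**Conclusion.** The point holds as an avoidable source of bias in the primary before/after comparison, of unknown size and possibly near zero. Its expected direction is to mask a PRP benefit, which matters because Section 1.2.1 sets out to demonstrate efficacy and only 10 people are enrolled. The direction rests on the protocol's own account of hydration. The power losses in the working show sensitivity to assumed shifts and do not estimate what will happen. The problem arises only in participants who use moisturizers or oils up to baseline, and it is specific to the within-group test: randomization of nails within a person protects a PRP-versus-PPP contrast from any shift common to all ten nails. The documents do not support a claim that the trial is invalid or that PRP would be wrongly favoured.

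**What to change.** 1. Reconcile the pre-study product list in Sections 3.1 and 4.3 with the on-study list in Sections 3.1 and 4.4, so that the baseline and week 12-14 photographs are taken under the same product restrictions. The interval is for the sponsor to set; the protocol already uses 1 month for polish, though Section 4.3 omits it.
2. State that the Visit 1 photograph is the baseline, and define when the study period begins.
3. Allow Visit 1 on the screening day only for participants who already meet the reconciled restriction.
4. Record the last use of moisturizers and oils at screening.
5. In Section 12.1, report the within-participant PRP-minus-PPP change alongside the before/after change.

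**Cost.** Items 1 to 4 need wording changes and one screening question. Some participants would wait longer before Visit 1, and would be off these products for longer, within a one-year enrolment period for 10 participants. Item 5 needs no new data but is imprecise with two control nails per person. With SD 1 and independent nails, the SD of a participant's difference is √(1/8 + 1/2) = 0.79, and a paired t-test on 10 participants has power 0.43 for a difference of 0.5. It should be reported with its confidence interval; it does not replace items 1 to 4.

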9.2.1.1 Assessment

9.2.1.2 Method of Assessment

9.2.1.3 Timing of Assessment

10. Measurement of Effect

PGA (Physician Global Assessment) Score:

The Principal Investigator will utilize the Physician Global Assessment (PGA) score for screening purposes during the screening/baseline visit to determine eligibility. The PGA will be comprised of five components: lamellar splitting, transverse splitting, ridging and longitudinal groove, longitudinal splitting, and nail thickness. Lamellar splitting, which represents onychoschizia, is defined as distal furrows or splits encompassing the distal nail plate involving the complete free edge of the nail plate. The second component, transverse splitting, is described as horizontal splitting from the free edge of the nail plate- with at least 2 or 3 horizontal splits of the distal nail plate. The third component, ridging and longitudinal grooves, is defined by at least 50% of the nail plate showing deep ridges and corresponding grooves. The fourth component, longitudinal splitting, which represents onychorrhexis, is defined as at least one deep longitudinal split of the entire nail plate. The fifth component, nail thickness, is defined by a clearly visible change in nail thickness. The presence of each of these components during the screening/baseline visit will represent 1 point on a scale. The inclusion criterion requires patients to have a score of at least 2 out of a maximum of 5 points. An independent blinded endpoint committee will assess change from baseline based on the PGA.

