10.1 Response Criteria

Change in the PGA from baseline.

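### The primary endpoint (PGIA) has no stated scale, and the only defined score behind it is a 0-5 present/absent screening count that registers improvement only across the moderate line and has two loosely worded items

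*Combined protocol and SAP*

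**What the plan says.** The protocol summary and sections 1.2.4, 3.1 and 12.1 name the PGIA as the primary endpoint, and section 7.11 has the blinded committee rate it. Section 3.1 says that it covers improvement in five features: lamellar splitting, transverse splitting, ridging and grooves, longitudinal splitting, and thickness. No section gives it a range, categories or anchors.

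The PGA covers the same five features and is defined. Section 3.1 introduces it as the Principal Investigator's screening score: "The presence of each of these components during the screening/baseline visit will represent 1 point on a scale", and "The inclusion criterion requires patients to have a score of at least 2 out of a maximum of 5 points". Its source is a published grading system in which "a grading system of 0-3 was used for each component, with 0-none, 1-mild, 2-moderate, 3-severe". On how the two relate, section 3.1 says: "The scale used for screening in the present study mirrors the moderate (score of 2) criteria used in the study".

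Section 10 repeats the PGA definition and adds: "An independent blinded endpoint committee will assess change from baseline based on the PGA". Section 10.1 gives one response criterion: "Change in the PGA from baseline". Section 12.1 sizes the study for a score change of 0.5 with SD 1, and names the PGA as the tool whose SD is uncertain.

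Some item definitions are floors. Ridging, for example, "is defined by at least 50% of the nail plate showing deep ridges and corresponding grooves". On thickness: "The fifth component, nail thickness, is defined by a clearly visible change in nail thickness". Transverse splitting needs a minimum of two or three horizontal splits, without saying which.

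**The concern.** A present/absent count cut at moderate suits an entry screen, where the question is whether a patient has enough disease. As an outcome it discards any change that stays on one side of the cut. Ridging that falls from 100% to 55% of the plate is present at both visits and scores no change. The loss would make a null result hard to interpret: either PRP did little, or the score could not show what it did.

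Two items also lack a fixed meaning at follow-up. The thickness definition does not say thicker or thinner, or changed from what. The transverse-split definition lets two readers apply different cuts to the same photograph.

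**Working it through.** **1. Which score is analysed.** Section 12.1 compares the PGIA at week 12-14 with its baseline value by paired t-test. That needs a score at each visit, and a rating of improvement has no baseline value. Of the instruments named for these five features, only the PGA yields a score per visit. The NSI in section 3.1 scores other surface signs apart from ridging, and no role is assigned to it. So the PGA count is the only defined candidate, and sections 10 and 10.1 name it.

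**2. The plan's own figure.** Inputs from section 12.1: difference 0.5, SD 1, two-sided 0.05, 90% power. The normal approximation gives (1.960 + 1.282)² / 0.5² = 10.51 / 0.25 = 42.0, so 43 nails. The noncentral t gives 44 (power 0.900), as stated. All six cells of the table reproduce (5, 13, 26; 13, 44, 97).

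**3. What the count registers.** Set present = grade 2 or 3. This is explicit for the three items with a floor (transverse splitting, ridging, longitudinal splitting) and a reading for lamellar splitting and thickness.

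| Improvement | Count before, after | Scores? |
|---|---|---|
| 1 to 0 | 0, 0 | no |
| 2 to 1 | 1, 0 | yes |
| 3 to 2 | 1, 1 | no |
| 2 to 0 | 1, 0 | yes |
| 3 to 1 | 1, 0 | yes |
| 3 to 0 | 1, 0 | yes |

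One of the three one-grade steps scores, and four of the six improving transitions.

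**4. How much is lost.** The documents give no grade distribution, so the inputs here are assumptions. Let p0 to p3 be the baseline shares of grades 0 to 3. If every improvement is one grade, the share of true improvements that register is p2 / (p1 + p2 + p3).

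For sensitivity, 400,000 nails per setting were simulated. Five independent items each improve one grade with probability 0.2 or 0.4. At both visits the observed grade moves by 1 with probability 0.1 each way, clipped to 0-3. The ratio is (mean/SD)² of the change in the 0-5 count, divided by the same quantity for the 0-15 graded sum.

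| Baseline mix, grades 0/1/2/3 (%) | Share registering | Ratio |
|---|---|---|
| 25/25/25/25 | 0.25/0.75 = 33% | 0.41-0.42 |
| 10/20/50/20 | 0.50/0.90 = 56% | 0.64-0.67 |
| 30/10/50/10 | 0.50/0.70 = 71% | 0.92-0.98 |
| 30/40/20/10 | 0.20/0.70 = 29% | 0.33-0.35 |

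The range is therefore about 0.3 to 1.0. Keeping only nails with an observed baseline count of at least 2 gives 0.51 to 1.11. That rule is itself an assumption, because the entry criterion is written per patient. Selecting on the noisy count also inflates its later fall, through regression to the mean.

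**The case against.** The strongest objection is that the endpoint is the PGIA. Section 3.1 confines the PGA to screening, and the sentence in section 10 could mean that the committee rates improvement across the PGA's features. A graded improvement rating would show a change from severe to moderate. This stands as a limit: the lost sensitivity follows from one resolution of a conflict in the protocol. It does not remove the point, because the PGIA has no scale and sections 10 and 10.1 say PGA.

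Four stronger readings are tempting, and the documents do not support them.

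- *Improvement in the worst nails goes unseen.* Severe to mild and severe to none both score; only steps that stay on one side of the cut are lost.
- *A given percentage of improved nails is missed.* Any such figure depends on assumed baseline grades and is not a bound. With re-grading noise at follow-up only, the 30/10/50/10 mix even favours the count (ratio 1.4 to 2.6). With noise at both visits that advantage disappears.
- *The trial is underpowered.* With SD held at 1 and nails treated as independent, capturing half of a 0.5-point change would raise 44 nails to 171, against the 80 PRP nails in section 12.2. But the captured share is unknown, and the planned 0.5 may already be on the count scale.
- *The thickness item penalises PRP.* That requires reading change as change since baseline. Departure from normal is the more natural sense at screening, so this is an ambiguity and not a demonstrated bias.

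It is also fair that the same cut applies to PRP and PPP nails, and that the documents do not supply the anchors for grades 1 and 3.

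**Conclusion.** The point holds in a limited form. The primary endpoint has no stated scale, and the only defined score on its features is a screening count that sections 10 and 10.1 reuse for response. Applied as written, the count registers one of three one-grade improvements and four of six improving transitions. This rests on present meaning moderate or worse.

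The cost is sensitivity. Its size is not known from the documents: the illustrative ratio runs from about 0.3, a large loss, to about 1.0, none. The thickness and transverse-split items need clearer wording whichever score is used. The sample-size arithmetic is sound. This is a cheap improvement and not a fatal flaw.

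**What to change.** - Reconcile PGA and PGIA in the summary and in sections 1.2.4, 3.1, 7.11, 10, 10.1 and 12.1, so that one named score with one stated range is the endpoint.
- Keep the 0-5 count, with its threshold of at least 2, for eligibility only.
- For response, have the same blinded committee grade each of the five features 0-3 per nail on the existing baseline and week 12-14 photographs. Use the graded system that the protocol already cites, with its anchors written into the reader form, and analyse change in the 0-15 sum.
- Define thickness as departure from normal, and state one number for the transverse-split cut.
- Restate the 0.5 difference and the SD of 1 on the new scale.

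The cost is protocol wording, a revised reader form and slightly more reading time, with no added visits, photographs or readers. The downside is that the planning values must be reset on a scale for which the documents give no SD. The committee should also check that thickness can be graded consistently from photographs.
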